
Objective: To compare anti-PnPs serotype-specific IgG geometric mean concentrations (GMCs) at 30 days following Dose 3 for participants administered V114 versus participants administered Prevenar 13TM. 
Hypothesis (H3): V114 is noninferior to Prevenar 13TM for the 13 shared serotypes between V114 and Prevenar 13TM based on anti-PnPs serotype-specific IgG GMCs at 30 days following Dose 3.
 
(The statistical criterion for non-inferiority requires the lower bound of the 2-sided 95% CI for anti-PnPs serotype-specific IgG GMC ratio [V114/ Prevenar 13TM] to be greater than 0.5).
 
Hypothesis (H4): V114 is superior to Prevenar 13TM for the 2 serotypes unique to V114 based on anti-PnPs serotype-specific IgG GMCs at 30 days following Dose 3.
 
(The statistical criterion for superiority requires the lower bound of the 2-sided 95% CI for anti-PnPs serotype-specific IgG GMC ratio [V114/ Prevenar 13TM] to be greater than 2.0).
	
Anti-PnPs serotype-specific IgG responses for the 15 serotypes contained in V114 at 30 days PD3

Objectives	Endpoints
Secondary	

 Objective: To compare the antigen-specific response rate to each antigen included in Vaxelis™ at 30 days following Dose 3 for participants administered V114 concomitantly with Vaxelis™ versus participants administered Prevenar 13™ concomitantly with Vaxelis™. 
Hypothesis (H5): Vaxelis™ administered concomitantly with V114 is non-inferior to Vaxelis™ administered concomitantly with Prevenar 13™ at 30 days following Dose 3 for each antigen included in Vaxelis™.
	
Antibody responses to:
 
 diphtheria toxoid tetanus toxoid pertussis toxin (PT) pertussis filamentous hemagglutinin (FHA) pertussis fimbriae 2/3 (FIM 2/3) pertussis pertactin (PRN) Haemophilus influenzae type b polyribosylribitol phosphate (Hib-PRP) hepatitis B surface antigen (HBsAg) poliovirus serotypes 1, 2, and 3 
at 30 days PD3 of V114 or Prevenar 13™

 Objective: To evaluate the anti-PnPs serotype-specific- IgG response rates and GMCs at 30 days following Dose 2 by each vaccination group. 	
 Anti-PnP serotype-specific IgG responses for the 15 serotypes contained in V114 at 30 days PD2

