4.2.1 Rationale for Endpoints

4.2.1.1 Immunogenicity Endpoints

The immunogenicity endpoints are consistent with previous studies evaluating PCVs and the concomitantly administered pediatric vaccines in this study.

The pneumococcal electrochemiluminescence (PnECL) assay and the multiplexed opsonophagocytic assay (MOPA) will be used to measure vaccine-induced, anti-PnPs serotype-specific immune responses for all 15 serotypes included in V114. PnECL measures serotype-specific IgG concentrations (primary endpoint based on GMCs), and MOPA measures serotype-specific OPA titers (secondary endpoint based on GMTs). OPA GMTs represent functional antibodies capable of inhibiting growth of *S pneumoniae* in culture. Additional information on the immunogenicity assays can be found in Section 8.2.

Several studies have shown a positive correlation between serotype-specific IgG antibody concentrations and OPA titers in children and adults [Centers for Disease Control and Prevention 2010] [Anttila, M., et al 1999] [Romero-Steiner, S., et al 1997]. Since MOPA requires more serum than the PnECL assay, the PnECL will be used to test the primary immunogenicity hypotheses in this study.

The use of the serotype-specific IgG antibody level of $\geq 0.35 \mu\text{g/mL}$ has been recommended by a WHO expert panel as an acceptable threshold value for evaluating the clinical performance of PCVs following a routine childhood vaccination regimen [World Health Organization 2008] [World Health Organization 2005]. The response rate (ie, the proportion of participants meeting the serotype-specific IgG threshold value of $\geq 0.35 \mu\text{g/mL}$) is a primary endpoint in this study.

Anti-PnPs serotype-specific IgG and OPA responses will be measured at 3 time points:

- Approximately 30 days following Dose 2 to evaluate the immune response to the primary vaccination series (IgG GMCs, IgG response rates, OPA GMTs, and OPA response rates)
- Immediately prior to Dose 3 to evaluate the persistence of protective immunity (IgG GMCs, OPA GMTs, and OPA response rates)
- Approximately 30 days following Dose 3 to evaluate anamnestic antibody responses (IgG GMCs, IgG response rates, OPA GMTs, and OPA response rates)

Measurement at 30 days following Dose 3 was selected for the primary endpoint, as this time point is considered the completion of the PCV series, where immune memory is boosted.

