9.1 Statistical Analysis Plan Summary

Key elements of the Statistical Analysis Plan are summarized below; the comprehensive plan is provided in Section 9.2 through Section 9.12.

Study Design Overview	A Phase 3, Multicenter, Randomized, Double-blind, Active-comparator-controlled Study to Evaluate the Safety, Tolerability, and Immunogenicity of a 3-dose Regimen of V114 in Healthy Infants (PNEU-PED-EU-2)
Treatment Assignment	Participants will be randomly assigned in a 1:1 ratio to V114 or Prevenar 13™, respectively.
Analysis Populations	Immunogenicity: Per-Protocol (PP) Safety: All Participants as Treated (APaT)
Primary Endpoint(s)	Immunogenicity: 
Anti-PnPs serotype-specific IgG response rates (proportion of participants meeting serotype-specific IgG threshold value of $\geq 0.35 \mu\text{g/mL}$) at 30 days PD3Anti-PnPs serotype-specific IgG GMCs at 30 days PD3 Safety: 
Proportion of participants with solicited injection-site AEs (swelling, redness/erythema, tenderness/pain, and hard lump/induration) from Day 1 through Day 14 following any vaccination with V114 or Prevenar 13™Proportion of participants with solicited systemic AEs (irritability, drowsiness/somnolence, appetite lost/decreased appetite, and hives or welts/urticaria) from Day 1 through Day 14 following any vaccination with V114 or Prevenar 13™Proportion of participants with vaccine-related SAEs from Day 1 through completion of study participation
Key Secondary Endpoints	
Antigen-specific responses for all antigens included in Vaxelis™ at 30 days PD3 of V114 or Prevenar 13™ for participants administered V114 concomitantly with Vaxelis™ versus participants administered Prevenar 13™ concomitantly with Vaxelis™Anti-PnPs serotype-specific IgG response rates (proportion of participants meeting serotype-specific IgG threshold value of $\geq 0.35 \mu\text{g/mL}$) and GMCs for the 15 serotypes contained in V114 at 30 days PD2

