Other secondary/exploratory objectives include the evaluation of anti-PnPs serotype-specific IgG GMCs at 30 days PD2 and Predose 3, anti-PnPs serotype-specific IgG response rates at 30 days PD2, and anti-PnPs serotype-specific OPA GMTs and response rates at 30 days PD2, Predose 3, and 30 days PD3. The evaluations of these objectives will be performed within each vaccination group separately. Descriptive statistics with point estimates and within-group 95% CIs will be provided. For the continuous endpoints, the point estimates will be calculated by exponentiating the estimates of the mean of the natural log values and the within-group CIs will be derived by exponentiating the bounds of CIs of the mean of the natural log values based on the 1-sample t-distribution. For the dichotomous endpoints, the within-group CIs will be calculated based on the exact method proposed by Clopper and Pearson [CLOPPER, C. J. and PEARSON, E. S. 1934].

Reverse Cumulative Distribution Curves for IgG concentrations at 30 days PD3 will be graphically displayed by serotype.

A detailed analysis strategy for immunogenicity endpoints is listed in [Table 6](#).

Table 6 Analysis Strategy for Immunogenicity Variables

Endpoint/Variable (Description, Time Point)	Primary vs. Supportive Approach [†]	Statistical Method	Analysis Population	Missing Data Approach
Primary Endpoint (H1 – H2)				
Anti-PnPs serotype-specific IgG response rates at 30 days PD3	P	Miettinen and Nurminen (estimate, 95% CI, p-value)	PP	Missing data will not be imputed
	S		FAS	
Primary Endpoint (H3 – H4)				
Anti-PnPs serotype-specific IgG GMCs at 30 days PD3	P	t-distribution with the variance estimate from a linear model [‡] (estimate, 95% CI, p-value)	PP	Missing data will not be imputed
	S		FAS	
Secondary Endpoint (H5)				
Antigen-specific response rates for all antigens included in Vaxelis TM at 30 days PD3 of V114 or Prevenar 13 TM	P	Miettinen and Nurminen (estimate, 95% CI, p-value)	PP	Missing data will not be imputed
	S		FAS	
	S		FAS	

Endpoint/Variable (Description, Time Point)	Primary vs. Supportive Approach [†]	Statistical Method	Analysis Population	Missing Data Approach
Other Secondary Endpoints				
Anti-PnPs serotype-specific IgG response rates and GMCs for the 15 serotypes contained in V114 at 30 days PD2	P	Descriptive Statistics (estimate, 95% CI)	PP	Missing data will not be imputed

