9.9 Sample Size and Power Calculations

9.9.1 Sample Size and Power for Immunogenicity Analyses

The study will randomize participants in a 1:1 ratio to the 2 vaccination groups. The overall sample size will be approximately 1180 with 590 participants into each vaccination group. The sample size was chosen to ensure sufficient power for the multiple endpoints across both primary and secondary hypotheses. It is assumed that approximately 472 participants per vaccination group will be evaluable for PP immunogenicity analyses at 30 days PD2 (based on an 80% evaluability rate), and approximately 443 participants per vaccination group will be evaluable for PP immunogenicity analyses at 30 days PD3 (based on a 75% evaluability rate).

With this study sample size and the assumptions listed below, the overall power for the primary hypotheses is >95% for demonstrating non-inferiority of V114 to Prevenar 13™ for the 13 shared serotypes and superiority for the 2 unique serotypes for V114 formulations. The overall power for the secondary hypotheses for concomitant antigens evaluation is ~90%. The power for individual hypothesis components is provided below.

For the primary immunogenicity endpoint/hypothesis (H1), the study has >95% power at a 1--sided 2.5% alpha level to demonstrate V114 is non-inferior to Prevenar 13TM at 30 days PD3 for anti-PnPs serotype-specific IgG responses at or above the threshold value of 0.35 µg/mL for the 13 shared serotypes between V114 and Prevenar 13TM based on the following assumptions: (1) an approximately 75% evaluability rate at PD3 as observed in previous Phase 2 V114 pediatric studies; (2) a non-inferiority margin of --0.1 for the difference (V114-Prevenar 13TM); and (3) underlying serotype-specific IgG response rates (proportion of participants meeting serotype-specific IgG threshold value of ≥ 0.35 µg/mL at 30 days PD3 of V114 or Prevenar 13TM) are 95% at 30 days PD3.

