For the primary immunogenicity endpoint/hypothesis (H2), the study has >95% power at a 1--sided 2.5% alpha level to demonstrate V114 is superior to Prevenar 13TM at 30 days PD3 for anti-PnPs serotype-specific IgG responses at or above the threshold value of 0.35 µg/mL for the 2 unique serotypes contained in V114 based on the following assumptions: (1) an approximately 75% evaluability rate at 30 days PD3 as observed in previous V114 pediatric Phase 2 studies; (2) a superiority margin of 0.1 for the difference (V114-Prevenar 13TM); and (3) underlying serotype-specific IgG response rates (proportion of participants meeting serotype-specific IgG threshold value of ≥ 0.35 µg/mL at 30 days PD3 of V114 or Prevenar 13TM) are 95% in V114 group and 2% in Prevenar 13TM group at 30 days PD3.

For the primary immunogenicity endpoint/hypothesis (H3), the study has >95% power at a 1--sided 2.5% alpha level to demonstrate V114 is non-inferior to Prevenar 13TM at 30 days PD3 for anti-PnPs serotype-specific IgG GMCs at 30 days PD3 based on the following assumptions: (1) an approximately 75% evaluability rate at 30 days PD3 as observed in previous V114 pediatric Phase 2 studies; (2) a non-inferiority margin of 0.5 (V114/Prevenar 13TM); (3) SD of anti-PnPs serotype-specific IgG GMCs in log scale is 1.1 as those observed in previous MSD studies, and (4) the true GMC ratio (V114/Prevenar 13TM) for anti-PnPs serotype-specific IgG GMCs is 1.0.

For the primary immunogenicity endpoint/hypothesis (H4), the study has >95% power at a 1-sided 2.5% alpha level to demonstrate V114 is superiority to Prevenar 13TM at 30 days PD3 for anti-PnPs serotype-specific IgG GMCs for the 2 unique serotypes contained in V114 based on the following assumptions: (1) an approximately 75% evaluability rate at PD3 as observed in previous Phase 2 V114 pediatric studies; (2) a superiority margin of 2.0 (V114/Prevenar 13TM); and (3) SD of anti-PnPs serotype-specific IgG GMCs in log scale is 1.1 as those observed in previous MSD studies, and (4) the true GMC ratio (V114/Prevenar 13TM) for anti-PnPs serotype-specific IgG GMCs is 10.0.

The study is considered to have met its primary objective if V114 is non-inferior to Prevenar 13TM for the 13 shared serotypes and superior to Prevenar 13TM for the 2 unique serotypes contained in V114.

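### Should the plan add a direct V114 versus Prevenar 13 comparison of IgG after Dose 2?

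*Combined protocol and SAP*

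**What the plan says.** Section 3 frames the IgG objectives 30 days after Dose 3 (PD3) as comparisons between arms, each with a hypothesis and a margin. The PD2 objective is framed differently: to evaluate "IgG response rates and GMCs at 30 days following Dose 2 by each vaccination group". Section 4.2.1.1 gives the purpose of the PD2 sample: "Approximately 30 days following Dose 2 to evaluate the immune response to the primary vaccination series". The same section explains that PD3 was chosen for the primary endpoint because it marks completion of the series.

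Section 9.6.1 follows that framing. For the other secondary and exploratory objectives it says "The evaluations of these objectives will be performed within each vaccination group separately", and then "Descriptive statistics with point estimates and within-group 95% CIs will be provided". GMCs get one-sample t intervals and response rates get Clopper-Pearson intervals. Table 6 has a row for "Anti-PnPs serotype-specific IgG response rates and GMCs for the 15 serotypes contained in V114 at 30 days PD2" with descriptive statistics as the method. The Section 9.1 summary places response rates "and GMCs for the 15 serotypes contained in V114 at 30 days PD2" under key secondary endpoints, while Table 6 files them under other secondary endpoints.

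For Vaxelis, Section 3 has an exploratory PD2 objective that sets V114 recipients against Prevenar 13 recipients with the word *versus*. The footnote to Table 5 carries the same 11 endpoints to PD2. Section 9.6.1 assigns the Miettinen-Nurminen (M&N) method to Vaxelis at PD3 only (H5).

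**The concern.** The trial is randomised, and PD2 is the one point at which the response to the two-dose primary series is measured. A reader will want to know whether V114 and Prevenar 13 differ there, serotype by serotype. The plan gives two separate intervals and leaves the comparison to the reader.

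Judging by whether two intervals overlap is a poor substitute. With 472 per arm and a log SD of 1.1, each arm's GMC interval is about ×/÷1.105. Two such intervals stop overlapping only when the ratio passes 1.105² ≈ 1.22, whereas a direct interval excludes 1 once the ratio passes about 1.15.

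The Vaxelis point looks sharper. Section 9.6.1 says that it covers exploratory objectives, yet it names no between-arm method for an objective worded as a between-arm one. At stake would be a prespecified estimate at PD2, and an objective left without a method.

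**Working it through.** **Inputs.** Section 9.9.1 gives 590 randomised per arm and 80% evaluability at PD2, hence "approximately 472 participants per vaccination group will be evaluable for PP immunogenicity analyses at 30 days PD2". It also states, for the PD3 power calculations, "SD of anti-PnPs serotype-specific IgG GMCs in log scale is 1.1 as those observed in previous MSD studies". The documents give no PD2 response rate and no PD2 SD, so both are assumptions below.

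**The plan's own figures.**
- PD2 sample size: 590 × 0.80 = 472. PD3: 590 × 0.75 = 442.5, stated as 443. Both agree.
- The plan states no power or precision at PD2. The nearest figure is the joint power of about 90.9% for H5 at PD3. The Farrington-Manning formula, one-sided 0.025, 443 per arm and independent antigens, gives 0.999995² × 0.9787⁴ × 0.9980⁵ ≈ 0.908 (2 antigens at 95%/−10 points, 4 at 97%/−5, 5 at 90%/−10). This agrees with the plan.

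**What a PD2 contrast would show.**
- GMC ratio: the half-width factor is exp(t × SD × √(2/n)). With t ≈ 1.9625 on 942 degrees of freedom, SD 1.1 and n = 472, this is exp(1.9625 × 1.1 × 0.0651) = exp(0.1405) = 1.151. A ratio of 1.0 would have a 95% CI of 0.87 to 1.15. For SD 0.9 and 1.3 the factors are 1.122 and 1.181.
- Response-rate difference: M&N half-widths with equal rates and n = 472 are about 2.9 points at 95%, 3.9 at 90%, 5.1 at 80%, 5.9 at 70% and 6.2 at 60%. The simple approximation at 90%, 1.96 × √(2 × 0.9 × 0.1/472) = 3.8 points, is close.

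**Can it be had from what is already planned?**
- GMC: the arm interval has log half-width t × SD/√n = 1.965 × 1.1/21.73 = 0.0995. This gives back the SD, and two arms combine to 0.0995 × √2 = 0.1407, or ×/÷1.151: the same answer. Rounding costs little. In 20,000 simulated results per GMC level, with GMCs and limits printed to two decimals, the 97.5th percentile of the relative error in the ratio's lower limit was 2.0% at a GMC of 0.5, 1.0% at 1, 0.5% at 2 and 0.25% at 4.
- Rates: one responder in 472 is 0.21 points. If n and a percentage to one decimal are printed, the count is fixed and the M&N interval can be computed exactly.

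**What the addition would cost.** 15 serotypes × 2 measures = 30 intervals, of which 4 concern 22F and 33F and add little. The 11 Vaxelis endpoints make 41. Read as tests under no difference, 30 × 0.05 = 1.5 or 41 × 0.05 ≈ 2 would exclude the null by chance.

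**The Vaxelis wording.** Table 5 fixes the PD2 endpoints and thresholds, so only the interval method is open. The missing Table 6 row carries little weight, since that table has no exploratory rows at all. Predose 3 IgG and PD2 OPA are absent too.

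**The case for a change.** The best case for a change is that it is cheap and harmless. M&N and the linear model for GMC ratios are already in the plan, no alpha or participants are needed, and H1 to H5 are untouched. Section 9.6.2 already accepts many unadjusted between-arm intervals for Tier 2 safety events as descriptive aids. PD2 has more evaluable infants than PD3 (472 against 443). Section 10.7.1.1 reports that an earlier V114 formulation gave infants lower responses than Prevenar 13 for some shared serotypes, so serotype-level differences are what readers will ask about. A prespecified, published ratio is easier to cite than one rebuilt by hand.

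All of that is true, and it shows that the contrast would be a reasonable optional extra. It does not show a fault. Section 10.7.1.1 also says that later formulations induced antibody levels comparable to Prevenar 13, and its earlier observation concerns PD3, where this trial does compare the arms. The gain is convenience. Adding the contrasts would also mean rewording the within-group sentence in Section 9.6.1, which would otherwise contradict them.

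The Vaxelis point stands as a wording gap. The list of objectives under the within-group rule is introduced as what those objectives *include*. Read as open-ended, it would sweep in Vaxelis at PD2 and sit awkwardly with *versus*. The supplemental SAP mentioned in Sections 9 and 9.10 was not among the documents reviewed and may settle this.

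**Conclusion.** No change to the plan. The within-arm analysis of PD2 IgG is consistent from objective to method to table, and it appears deliberate: the arms are compared at PD3, where the series is complete. No stated figure, error rate or conclusion would alter if the contrast were added. A reader who wants it can recover the GMC ratio limits to within about 1% at a GMC of 1.0 (2% at 0.5), and the rate differences from the counts.

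The Vaxelis matter is a gap that analysts fill sensibly. The endpoints are fixed, the natural method is the one used for the same endpoints at PD3, and the analysis is exploratory with no margin attached.

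The sizes quoted rest on the PD3 log SD of 1.1 holding at PD2 (×/÷1.12 to ×/÷1.18 for SD 0.9 to 1.3) and on assumed PD2 response rates. The conclusion does not depend on them. It rests on the agreement between objective and method, and on arm-level n, estimates and intervals being reported with ordinary rounding.

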9.6.2 Statistical Methods for Safety Analyses

Safety and tolerability will be assessed by clinical review of all relevant parameters including AEs and postvaccination temperature measurements. Additional summaries on key safety parameters will also be provided following each vaccination.

The analysis of safety results will follow a tiered approach (Table 7). The tiers differ with respect to the analyses that will be performed. Adverse events (specific terms as well as system organ class terms) are either pre-specified as “Tier 1” endpoints, or will be classified as belonging to “Tier 2” or “Tier 3” based on the number of events observed.

Tier 1 Events

Safety parameters or AEs of special interest that are identified constitute “Tier 1” safety endpoints that will be subject to inferential testing for statistical significance with p-values and 95% CIs to be provided for between-treatment differences in the proportion of participants with events; these analyses will be performed using the Miettinen and Nurminen (M&N) method (1985), an unconditional, asymptotic method. However, these p-values and CIs should be regarded as helpful descriptive measures to be used in review, not formal methods for assessing the statistical significance of the between-treatment differences in AEs. For this protocol, solicited injection-site AEs (redness/erythema, swelling, hard lump/induration, and tenderness/pain) from Day 1 through Day 14 postvaccination and solicited systemic AEs (irritability, drowsiness, hives or welts, and appetite loss) from Day 1 through Day 14 postvaccination are considered Tier 1 events.

Tier 2 Events

Tier 2 parameters will be assessed via point estimates with 95% CIs provided for differences in the proportion of participants with events (also via the M&N method [1985]) [Miettinen, O. and Nurminen, M. 1985].

Membership in Tier 2 requires that at least 4 participants in any treatment group show the event. The threshold of at least 4 events was chosen because the 95% confidence interval for the between-group difference in percent incidence will always include zero when treatment groups of equal size each have less than 4 events and thus would add little to the interpretation of potentially meaningful differences. Because many 95% CIs for Tier 2 events may be provided without adjustment for multiplicity, the CIs should be regarded as a helpful descriptive measure to be used in review, not a formal method for assessing the statistical significance of the between-group differences in AEs.

In addition to individual events that occur in 4 or more participants in any treatment group, the broad AE categories consisting of the proportion of participants with any AE, a vaccine-related AE, an SAE, a vaccine-related SAE, discontinuation due to an AE, and death will be considered Tier 2 endpoints. The proportion of participants with maximum temperature measurements meeting the Brighton Collaboration cut points (Days 1 to 7) will also be considered Tier 2 endpoints.

Tier 3 Events

Safety endpoints that are not Tier 1 or 2 events are considered Tier 3 events. Only point estimates by treatment group are provided for Tier 3 safety parameters.

Table 7 Analysis Strategy for Safety Parameters

Safety Tier	Safety Endpoint [†]	p-Value	95% CI for Between-Group Comparison	Descriptive Statistics
Tier 1	Injection-site redness/erythema (Days 1 to 14)	X	X	X
	Injection-site swelling (Days 1 to 14)	X	X	X
	Injection-site tenderness/pain (Days 1 to 14)	X	X	X
	Injection-site hard lump/induration (Days 1 to 14)	X	X	X
	Irritability (Days 1 to 14)	X	X	X
	Drowsiness/somnolence (Days 1 to 14)	X	X	X
	Hives or welts/urticaria (Days 1 to 14)	X	X	X
	Appetite loss/decreased appetite (Days 1 to 14)	X	X	X

Safety Tier	Safety Endpoint [†]	p-Value	95% CI for Between-Group Comparison	Descriptive Statistics
Tier 2	Any AE [†]		X	X
	Any Vaccine-Related AE [†]		X	X
	Any SAE [†]		X	X
	Any Vaccine-Related SAE [†]		X	X
	Discontinuation due to AE [†]		X	X
	Death [†]		X	X
	Maximum temperature measurements meeting the Brighton Collaboration cut points (Days 1 to 7)		X	X
Tier 3	Specific AEs by SOC and PT [‡] (incidence ≥ 4 participants in one of the vaccination groups)		X	X
	Specific AEs by SOC and PT [‡] (incidence < 4 participants in all of the vaccination groups)			X

AE = adverse event; CI = confidence interval; PT = preferred term; SAE = serious adverse event; SOC = system organ class; X = results will be provided

[†] These endpoints are broad AE categories. For example, descriptive statistics for the safety endpoint of “Any AE” will provide the number and percentage of participants with at least one AE.

[‡] Includes only those endpoints not pre-specified as Tier 1 or not already pre-specified as Tier 2 endpoints.

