8.3.3 Safety Assessment and use of the eVRC

All participants will be observed for at least 30 minutes after each vaccination for any immediate reactions. If any immediate AEs are observed during this period, the time at which

the event occurred within this timeframe, as well as the event itself, any concomitant medications that were administered, and resolution of the event, must be recorded on the appropriate eCRF.

The limb that was used for the administration of V114 or Prevenar 13TM will be recorded in the eVRC (Note: the study will report injection-site AEs from V114 or Prevenar 13TM only; the location of V114 or Prevenar 13TM administration can be used by the participant or participant's legally acceptable representative to monitor the appropriate limb for injection-site AEs related to V114 or Prevenar 13TM).

Participant's legally acceptable representative will use the eVRC (Section 8.1.9) to document the following information:

- Rectal temperatures measured Day 1 (day of vaccination) through Day 7 following each vaccination; Day 8 through Day 14 following each vaccination if fever is suspected.
- Solicited injection-site AEs (swelling, redness, pain or tenderness, and hard lump) Day 1 through Day 14 postvaccination.
- Solicited systemic AEs (irritability, drowsiness, appetite lost, and hives or welts) Day 1 through Day 14 postvaccination.
- Any other unsolicited injection-site or systemic AEs Day 1 through Day 14 postvaccination.
- Use of any analgesic or antipyretic on the day of vaccination.
- Concomitant medications and nonstudy vaccinations Day 1 to Day 14 postvaccination.

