9.4.2 Safety Endpoints

Safety and tolerability will be assessed by clinical review of all relevant parameters including AEs and postvaccination temperature measurements following any vaccination with V114 or Prevenar 13™.

The safety analysis endpoints include:

- Proportion of participants with solicited injection-site AEs (swelling, redness/erythema, tenderness/pain, and hard lump/induration) from Day 1 through Day 14 following any vaccination with V114 or Prevenar 13™
- Proportion of participants with solicited systemic AEs (irritability, drowsiness/somnolence, hives or welts/urticaria, and appetite loss/decreased appetite) from Day 1 through Day 14 following any vaccination with V114 or Prevenar 13™
- Proportions of participants with the broad AE categories consisting of any AE and a vaccine-related AE from Day 1 through Day 14 following any vaccination with V114 or Prevenar 13™
- Proportions of participants with an SAE, a vaccine-related SAE, and discontinuation due to an AE, and death from Day 1 through 6 months following the vaccination with V114 or Prevenar 13™

- Participants body temperature measured Day 1 (day of vaccination) through Day 7 following any vaccination with V114 or Prevenar 13™

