optimization, 2 formulations of V114 (Formulation A and Formulation B) were tested clinically in several Phase 1/2 clinical studies involving a small number (20 to 50 subjects per arm) of young adults (18 to 49 years of age) and infants (V114-004 and V114-005), as well as larger number (125 to 230 subjects per arm) of pneumococcal vaccine-naïve adults 50 years of age and older (V114-006) and adults 65 years of age or older with prior history (at least 1 year prior to study entry) of vaccination with PNEUMOVAX™23 (V114-007). Both V114 formulations displayed an acceptable safety profile and induced comparable levels of antibodies to Prevenar 13™ for the shared serotypes. V114 also induced higher antibodies to serotypes 22F and 33F, which are not included in Prevenar 13™ and have emerged recently as important causes of pneumococcal disease in both children and adults. Results from these studies identified a formulation (Formulation B) with improved clinical performance in both infants and older adults. A pediatric Phase 2 study (V114-008) involving 1050 infants (350 per arm) is ongoing to confirm the performance of Formulation B observed in V114-005. Following vaccination with V114 Formulation B, the most frequently reported AEs were those solicited in the clinical study and included injection-site pain/tenderness (64% in infants and 60% in adults), redness (38% in infants and 11% in adults), and swelling (20% in infants and 16% in adults). Most frequently reported systemic AEs were those solicited in the studies; muscle pain (18%), fatigue (17%), headache (12%), and joint pain (7%) were commonly reported among adults, while irritability (82%), drowsiness (60%), decreased appetite (32%) were commonly reported in infants following any vaccination.

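### No aggregate comparison of unsolicited AEs is planned, and solicited reactions in 'any AE' would largely mask a moderate, diffuse unsolicited excess

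*Combined protocol and SAP*

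**What the plan says.** Section 8.3.3 has the legal representative record, as an item apart from the solicited reactions, "Any other unsolicited injection-site or systemic AEs Day 1 through Day 14 postvaccination".

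Section 9.4.2 lists as endpoints "Proportions of participants with the broad AE categories consisting of any AE and a vaccine-related AE from Day 1 through Day 14" after any vaccination. That is the same window as the solicited AEs. Section 9.6.2 gives between-group Miettinen-Nurminen 95% CIs to "the broad AE categories consisting of the proportion of participants with any AE, a vaccine-related AE, an SAE, a vaccine-related SAE", and also to discontinuation due to an AE, death and the temperature cut points. The Table 7 footnote says that descriptive statistics for 'any AE' "will provide the number and percentage of participants with at least one AE"; nothing excludes solicited events. No unsolicited category appears in 9.4.2, 9.6.2 or Table 7.

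The plan does go below the broad categories. "Adverse events (specific terms as well as system organ class terms) are either pre-specified" as Tier 1, or tiered by observed count, and an event in at least 4 participants in a group gets a 95% CI. Rarer events get point estimates by group.

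On background rates, Section 10.7.1.1 reports for Formulation B that "irritability (82%), drowsiness (60%), decreased appetite (32%) were commonly reported in infants following any vaccination". For the earlier V114 it gives irritability at 86%.

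**The concern.** Of the broad Tier 2 categories, only 'any AE' and 'vaccine-related AE' cover nonserious events in general. If most infants already count as an 'any AE' case because of a prompted reaction, the category mainly repeats what Tier 1 compares symptom by symptom and says little about unprompted events. Similar 'any AE' rates could then be read as a similar overall AE profile while unsolicited AEs differed. Safety is a primary objective of the study, and Section 4.2.1.2 says its data feed the V114 safety database for initial licensure in infants.

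**Working it through.** **Inputs from the documents.** There are 590 participants per arm, a two-sided 5% level and full evaluability for safety (9.9.2). Table 9 shows pairs of AE rates detectable with about 80% probability. Irritability in infants was 82% and 86% (10.7.1.1).

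**Assumptions.** S is the share of infants with at least one solicited AE, equal in both arms. Unsolicited AEs occur at rates u0 and u1, independently of solicited ones. The documents give no unsolicited rate, so Table 9's last row (30% versus 37.7%) serves as a benchmark. In the earlier data S was at least the irritability rate, but this trial may differ, so S runs from 60% to 95%.

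**Step 1: reproduce Table 9.** Normal-approximation power with pooled variance under the null and no continuity correction, counting intervals that exclude zero in the harmful direction:

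power = Φ[(d − 1.96 × SE_null) / SE_alt], where d is the rate difference.

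For 30% versus 37.7%, d = 0.077, SE_null = √(2 × 0.3385 × 0.6615 / 590) = 0.02755 and SE_alt = √[(0.30 × 0.70 + 0.377 × 0.623) / 590] = 0.02746. Power is Φ(0.84) = 79.9%. Across the seven rows of Table 9 the results are 79.6% to 80.3%, so the table reproduces.

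**Step 2: the same excess inside 'any AE'.**

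P(any AE) = S + (1 − S) × u, so the difference shrinks to (1 − S)(u1 − u0).

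At S = 82% the rates are 0.82 + 0.18 × 0.30 = 87.4% and 0.82 + 0.18 × 0.377 = 88.8%. The difference is 0.18 × 7.7 = 1.4 points.

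| S | 'Any AE', 30% v 37.7% unsolicited | Difference (points) | Power |
|---|---|---|---|
| 60% | 72.0% v 75.1% | 3.1 | 22.3% |
| 82% | 87.4% v 88.8% | 1.4 | 11.0% |
| 86% | 90.2% v 91.3% | 1.1 | 9.3% |
| 90% | 93.0% v 93.8% | 0.8 | 7.7% |
| 95% | 96.5% v 96.9% | 0.4 | 5.6% |

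At S = 82%, 'any AE' reaches 80% power only if unsolicited AEs rise from 30% to about 57%.

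**Step 3: what the SOC intervals recover.** Spread the 30% versus 37.7% excess evenly over k independent SOCs, with per-SOC rate 1 − (1 − u)^(1/k).

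| k | Rate per SOC | Power per SOC | At least one CI excludes zero |
|---|---|---|---|
| 1 | 30.0% v 37.7% | 79.9% | 79.9% |
| 3 | 11.2% v 14.6% | 41.0% | 79.5% |
| 5 | 6.9% v 9.0% | 27.5% | 79.9% |
| 8 | 4.4% v 5.7% | 19.1% | 81.6% |

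With no true difference, the chance that at least one of k such intervals excludes zero in the harmful direction is 1 − 0.975^k: 7% for k = 3, 12% for 5 and 18% for 8. A single unsolicited row would carry 2.5%.

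**The case against.** The strongest reply is that the plan already looks beneath the broad categories. A SOC row pools many terms, and step 3 shows that some SOC interval would exclude zero about as often as a single pooled row would. A reader might infer from the missing category that an overall unsolicited excess would go unseen. The documents do not support that: a concentrated excess would show in its SOC or term, and several SOCs leaning the same way could be noticed in the clinical review that 9.6.2 describes. What remains is that a diffuse signal must be picked out of many unadjusted intervals, with no single figure to summarise it. The Table 7 footnote also leaves open whether SOC totals exclude solicited terms; any that include them are diluted in the same way.

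Other replies limit the point:

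- The 82% comes from Formulation B studies that Section 10.7.1.1 describes as having 20 to 50 subjects per arm. That section also describes a 4-dose infant regimen in the earlier programme, against 3 doses here, so a cumulative rate may be lower. The 60% row allows for this, and power is still only 22%.
- Section 9.6.2 plans further summaries of key safety parameters after each vaccination. If these include 'any AE', each dose is no more saturated than the cumulative figure. The section does not say which parameters are covered.
- The intervals are labelled descriptive, and the primary safety endpoints are solicited AEs and vaccine-related SAEs. No hypothesis or primary endpoint is affected. Power is used here only to measure how much information 'any AE' carries.

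**Conclusion.** The point stands as a gap in reporting. Unsolicited AEs are collected but never aggregated, and 'any AE' is a poor substitute: an excess with about 80% power on its own has about 11% inside it at a solicited rate of 82%, and 22% at 60%. These sizes rest on equal solicited rates in both arms, on independence and on an assumed unsolicited rate. If the excess fell mainly on infants with no solicited reaction, more of it would come through.

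The loss is one overall comparison, chiefly for a diffuse excess. Serious events, discontinuations and deaths have their own rows, and nonserious solicited reactions do not swamp the counts of SAEs or deaths.

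A reader might also infer that 'vaccine-related AE' sits near its ceiling. The documents do not show this. Relatedness is an investigator judgement and no related-AE rate is given, so the masking applies there only as far as solicited events are judged related.

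**What to change.** In 9.4.2, 9.6.2 and Table 7, keep the existing categories and add two Tier 2 rows: any unsolicited AE (Days 1-14) and any vaccine-related unsolicited AE (Days 1-14). Give each a Miettinen-Nurminen 95% CI, after any vaccination and by dose.

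Define unsolicited as any AE outside the solicited list in 8.3.3, and state whether fever counts. Fever is not on that list, but it is prompted by the daily temperatures of Days 1-7 (8.3.2) and already compared through the Brighton cut points, so leaving this open would blur the new rows.

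The data are already collected, and no visit, procedure or hypothesis changes. Section 9 allows non-confirmatory analyses to be changed before unblinding through a supplemental SAP; doing so would make the rows pre-specified. The downside is two more unadjusted descriptive intervals in the main table, plus their by-dose counterparts.
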